Analysis approach

Statistical analysis will be performed by Stata, version 15. The baseline characteristics will be assessed by arm. The primary analysis will be an intention-to-treat (ITT) analysis. We will compare the mean length velocity (cm/ month) (primary outcome), weight velocity (gm/kg/day), LAZ, WLZ, and WAZ between the two intervention arms and the control arm using ANOVA, with the model adjusted for the birth weight and age of the infants at enrollment. If an outcome is missing for the intention-to-treat infants, the means from that group will be imputed.

Safety outcomes

i. Maternal serious adverse events

The occurrence of maternal SAEs will be expressed as the proportion of women with at least one SAE during the follow-up period (from enrolment to 179th day). The proportion will be calculated by dividing the number of women with at least one recorded SAE by the total number of enrolled participants. Results will be shown both as proportions of participants with any SAE as well as tabulated by the SAE category (death, hospitalization, other). If any participant has experienced more than one type of SAE, the participant will be recorded in each category.

ii. Infant serious adverse events

The occurrence of infant SAEs will be expressed as the proportion of babies with at least one SAE during the follow-up period (from enrolment to 179th day). The proportion will be

calculated by dividing the number of babies with at least one recorded SAE by the total number of recorded newborns. Results will be shown both as proportions of participants with any SAE as well as tabulated by the SAE category (death, hospitalization, other). If any participant has experienced more than one type of SAE, the participant will be recorded in each category.

Interim analysis

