11. SAMPLE SIZE CALCULATIONS & POWER ANALYSIS

The sample size is calculated and powered to look at multiple comparisons, between arms A and B, A and C plus B and C with a hypothesized higher increase with addition of Azithromycin to infant with Afzaaish in LW. Also, adjustment for multiple comparison is needed. Thus, calculations for the sample size is estimated and are per arm sample size is provided below based on the primary outcome of length velocity in LW trial with 1-sided testing, alphas to account for multiple comparison (the lower alpha), and drop out of 14% is assumed in the trial.

Assumptions for Sample Size Calculations

Variable	Difference	Std Dev	Alpha	Drop out portion	n/arm	n/arm adj dropout	Actual Power
Length Velocity	0.12	0.5	0.025	0.14	274	319	0.801

Based on assumptions, a sample size of 319 children per arm is calculated, assuming 14% drop out rate (i.e. 10% margin for loss to follow up, and 4% infants deaths).

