The null hypothesis for this trial is that the mean difference in length velocity between an infant of a lactating woman receiving standard breastfeeding counseling with BEP alone (Intervention arm 1) for 6 months or in combination with a single prophylactic dose of azithromycin at 42 days of age (Intervention arm 2) and an infant of a lactating woman receiving standard breastfeeding counseling alone (control arm) is equal or less than 0.12 cm/month (primary outcome). Due to the absence of evidence of such interventions on length velocity, we based this hypothesis on our local experience and field data from our field sites. The alternate hypothesis for this trial is that an infant of a lactating woman receiving BEP alone for 6 months or in combination with a single prophylactic dose of azithromycin at 42 days of age has a mean length velocity is greater than 0.12 cm/month that of an infant of a lactating woman not receiving an intervention at 6 months. The sample size takes multiple comparisons into account and is based on the primary outcome of length velocity with an effect size of difference of 0.12 cm per month between the arms (i.e., 0.72 cm difference at 6 months), a 1-sided test, power of 80% and an alpha of 0.025 to account for multiple comparisons (the lower alpha – Bonferroni correction was used). A drop-out rate of 14% (i.e., 10% loss to follow up and infant mortality rate of 4%) is assumed in the study, so the minimum total sample size required is 957 (319 lactating women in each arm).

7. Eligibility criteria

Inclusion Criteria

- a) Lactating women with a mid-upper-arm-circumference (MUAC) of < 23.0 cm
- b) Infants with a live birth outcome, captured within 168 hours (0-6 days)
- c) Individuals with the intention to stay in the catchment area for entire duration of trial after enrollment
- d) Individuals with the intention to exclusively breastfeed child for at least 6 months of age
- e) Individuals who have provided voluntary written informed consent

Exclusion Criteria

- a) Newborns with a birth weight of less than 1500 grams
- b) Newborns with a known congenital anomaly or other severe illness based on the study physician's assessment before enrollment.
- c) Lactating women with known allergies to peanut, lentils, chickpea or dairy products
- d) Individuals who were previously enrolled in the trial

8. Blinding

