10.1. Primary growth outcome*

- **'Length velocity (cm/month) of infant'** at 6 months is define as = $(\text{Length at 6-month visit} - \text{Length at baseline}) / (\text{Date of visit of visit at 6-month} - \text{Date of enrollment}) * 30.4$. (3)

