The primary analysis will be by intention-to-treat (ITT) perform for those who had anthropometry at 6 months. All analyses will be done using Stata software version 16. The WHO 2009 Child Growth Standards will be used for age-sex standardization of child length, weight, head circumferences, MUAC and weight-for-height. Descriptive analysis of each arm will be conducted, and percentages or continuous data with SD will be reported.

The baseline characteristics will be assessed by arm. Outcomes of mean length velocity, growth velocity, weight gain, z scores and change in z score from 0-6 month will be compared using one way analysis of variance (ANOVA). Tukey's test will be used for multiple comparisons. As determined *a priori* the analysis will be adjusted for the birth weight and length of infant, maternal MUAC at enrollment, maternal age, gravida, maternal body mass index and gender of child using general linear model (GLM). Mixed model analysis will be used to compare change in outcome per month in the intervention arm compared to the control arm. Using repeated measures ANOVA, the analysis will report beta coefficients and 95% CI. The coefficients represents the rate of change in outcome per month. For covariate adjustment, an unadjusted and stepwise adjusted model will be run. Trajectories will be plotted for mean length and weight by age for each arm, and monthly z scores were also be plotted.

13. Potential sub-group analysis

The following variables will be considered for sub-group analysis for primary and secondary outcomes:

1. Birth weight i.e. <2500 gm and => 2500 gm
2. Maternal MUAC at enrolment i.e. < 21.0 cm and =>21.0 cm
3. Maternal age i.e. <30 years and => 30 years
4. Gravidity i.e. <3 and =>3
5. Maternal BMI i.e. <18.5 kg/m² and =>18.5 kg/m²
6. Gender of child

14. Missing Data

We will treat missing data as it is, no imputation will be applied. We discussed that due to growth flattering during this age, imputation maybe unreliable.

15. Interim analysis

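### The SAP lists several models for length velocity without saying which one decides, and the protocol gives another; if the unadjusted ANOVA decides, the precision from the planned baseline-length adjustment is lost

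*SAP*

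**What the plan says.** SAP section 10.1 defines length velocity as 6-month length minus "Length at baseline", divided by the days between the two visits and multiplied by 30.4. The primary outcome is thus a change from baseline on a monthly scale.

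SAP section 12 calls the intention-to-treat analysis primary and then describes these analyses:

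- Mean length velocity, with other outcomes, "will be compared using one way analysis of variance (ANOVA"). The next sentence assigns multiple comparisons to Tukey's test.
- "the analysis will be adjusted for the birth weight and length of infant, maternal MUAC at enrollment, maternal age, gravida", together with maternal BMI and the child's sex, by GLM. This adjustment is described as fixed in advance.
- A mixed model for monthly change in outcome against control, with coefficients reported from repeated measures ANOVA.
- For covariate adjustment, an unadjusted model and a stepwise adjusted one.

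No sentence says which of these decides the primary comparison. The shell of SAP Table 3 has one pairwise-difference column and one p-value column, and names no covariates.

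Protocol section 10 (Analysis approach) gives a single model, an ANOVA comparing the two intervention arms with control, "with the model adjusted for the birth weight and age of the infants at enrollment". It does not list baseline length. The SAP's GLM lists baseline length and omits age at enrolment.

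**The concern.** The word primary in SAP section 12 settles the population, not the model. The SAP's routes and the protocol's model can give different p-values for the same comparison, and nothing fixes in advance which one counts. The stepwise step widens the choice, since neither its selection rule nor its candidate covariates are stated.

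The order of the text makes the unadjusted ANOVA a plausible default. It is named first, and the only multiplicity method in section 12 follows it directly. Baseline length is a component of the outcome and is scheduled for every infant within 0-6 days of birth. If the one-way ANOVA decides, any outcome variance that baseline length explains stays in the error term, although the SAP already plans a model that would remove it.

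**Working it through.** **Inputs from the documents.** The SAP gives an "effect size of difference of 0.12 cm per month between the arms" and "a 1-sided test, power of 80% and an alpha of 0.025 to account for multiple comparisons". The protocol's sample-size row reads "Length Velocity 0.12 0.5 0.025 0.14 274 319 0.801": SD 0.5 cm/month, 274 per arm before dropout, 319 after, power 0.801.

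**Step 1: reproduce the plan's figure.** The standard error of a pairwise difference is 0.5 × √(2/274) = 0.0427, so the noncentrality is 0.12/0.0427 = 2.81. The noncentral t test at one-sided 0.025 has power 0.801, and 274/(1 − 0.14) = 318.6, rounded up to 319. Both match. The calculation is for an unadjusted two-group comparison.

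**Step 2: the same data under Tukey's test.** With three arms of 274 the critical value is 2.348, equivalent to about one-sided 0.0096 for a single pair. Power for one pairwise difference of 0.12 is 0.68.

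**Step 3: effect of adjusting for baseline length.** Let ρ be the correlation of baseline and 6-month length, and k the ratio of the 6-month SD to the baseline SD. The interval between visits is treated as nearly constant. In units of the baseline variance:

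- variance of the change: 1 + k² − 2ρk
- residual variance given baseline length: k²(1 − ρ²)
- variance ratio: f = k²(1 − ρ²)/(1 + k² − 2ρk)

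With k = 1 this reduces to (1 + ρ)/2. The residual SD is 0.5√f. The documents give neither ρ nor k, so every row after the first rests on assumed values.

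| k | ρ | f | residual SD | power, one-sided 0.025 | power, Tukey |
|---|---|---|---|---|---|
| unadjusted | – | 1 | 0.500 | 0.801 | 0.678 |
| 1.00 | 0.24 | 0.620 | 0.394 | 0.945 | 0.888 |
| 1.00 | 0.50 | 0.750 | 0.433 | 0.899 | 0.815 |
| 1.00 | 0.70 | 0.850 | 0.461 | 0.860 | 0.758 |
| 1.25 | 0.24 | 0.750 | 0.433 | 0.899 | 0.814 |
| 1.25 | 0.50 | 0.893 | 0.472 | 0.843 | 0.734 |
| 1.25 | 0.70 | 0.981 | 0.495 | 0.808 | 0.687 |
| 1.50 | 0.24 | 0.838 | 0.458 | 0.865 | 0.764 |
| 1.50 | 0.50 | 0.964 | 0.491 | 0.815 | 0.696 |
| 1.50 | 0.70 | 0.998 | 0.499 | 0.802 | 0.679 |

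**Step 4: the sign of the correlation.** Velocity is negatively correlated with baseline length only when ρk < 1. At ρ = 0.7 and k = 1.5, ρk = 1.05; the correlation is slightly positive (about 0.05) and the gain almost vanishes.

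**Step 5: the cost.** The one-way ANOVA on 822 infants has 819 residual degrees of freedom. The SAP's seven covariates plus age at enrolment, one degree of freedom each, leave 811.

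**The case against.** The strongest reply is that the SAP already handles this. Shortly after the ANOVA sentence it commits in advance to a GLM that includes infant length, and that sentence can be read as describing the comparison just named. This stands in part. A reader might infer that the SAP forgoes baseline-length adjustment altogether; the text does not support that. What the reply does not supply is a statement that the GLM decides, and the later unadjusted and stepwise models count against assuming so.

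It is also fair to say that the protocol, taken alone, is not ambiguous, since it gives one model for the primary outcome. The ambiguity lies within the SAP and between the SAP and the protocol.

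A reader might infer that an unadjusted change score biases the comparison. It does not. Under randomisation the one-way ANOVA is valid, its standard error allows for chance imbalance in birth length, and the planned 80% power at one-sided 0.025 reproduces without adjustment. Nor does the definition of velocity by itself guarantee a negative correlation with baseline length; step 4 shows that this is conditional.

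The gains are measured against the fully unadjusted ANOVA. Part of them may already be captured by the protocol's birth-weight adjustment, and the documents do not allow that part to be computed. The 0.68 under Tukey reflects a stricter critical value than the sample-size calculation used. That is a separate matter from covariate adjustment, so only the movement within the Tukey column bears on this point. Omitting age at enrolment from the SAP list is minor on its own, because enrolment spans 0-6 days and velocity divides by actual elapsed time.

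**Conclusion.** The point holds as one of designation and efficiency. The SAP does not say which of its models decides length velocity, and the protocol specifies a model with different covariates. Adjustment for baseline length is planned, but its benefit is lost if the one-way ANOVA is taken as decisive, and the choice remains open after results are seen.

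The benefit cannot be pinned down from the documents. Over the assumed range it runs from almost nothing to about 14 percentage points of power at one-sided 0.025 (0.80 to 0.95 before rounding: 0.801 to 0.945), and from almost nothing to about 21 points under Tukey's critical value (0.678 to 0.888). These figures assume 274 analysed infants per arm, SD 0.5 and a true difference of 0.12. The case for naming one model does not depend on where in that range the truth lies. The change should be made; it does not call the validity of the trial into question.

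**What to change.** Name one primary analysis in SAP section 12: the GLM of length velocity on arm with baseline length, birth weight, sex, maternal MUAC, maternal age, gravidity and maternal BMI, as already listed, plus the protocol's infant age at enrolment. Fix the covariates and use no stepwise selection for the primary test. Take the multiplicity-adjusted pairwise contrasts from this model. Label the one-way ANOVA and the mixed and repeated-measures models as supporting.

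Align protocol section 10 with this, and have the SAP Table 3 shell state that the difference and p-value come from the adjusted model. Record the choice before the treatment codes are revealed.

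The cost is wording in the two documents and about eight of 819 residual degrees of freedom. The listed covariates come from enrolment, so no new data are needed.

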6.3. Inclusion and exclusion criteria

Inclusion Criteria

1. Live birth, captured within 0-6 days
2. MUAC of mother < 23.0 cm
3. Permanent resident of the catchment area, i.e. resident since last the 6 month at least (not temporary migrant or guest/relative)
4. Confirmed intention to exclusively breastfeed their child for at least 6 months of age
5. Child continues to stay with mother for the next six months
6. Provision of written informed consent

Exclusion Criteria

1. Working and employed lactating women staying away from the baby and the house, as exclusive breastfeeding is a prerequisite for enrollment in this trial
2. VLBW i.e. < 1500 gram
3. A mother who is unable to breastfeed the child due to certain medical conditions.
4. Child with congenital abnormalities (example: Cleft palate/lip, hydrocephalus, microcephalus, intestinal obstruction, etc.) or other serious illness at the time of enrollment, which was identified by the study physician (suspected sepsis for example)
5. Previously enrolled in this trial or PW trial
6. Known allergy to food items like, peanut, lentils, milk etc.

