6.5. Enrollment of Lactating Women

LW will be enrolled in the project based on case definition (inclusion criteria) and eligibility assessment. The research team will identify potentially eligible candidates during pregnancy and wait till the birth outcome to visit the household within 0-6 days of live birth to confirm eligibility. When the birth outcome is reported, following eligibility assessments, LWs will be enrolled in the trial after all key procedures of consent and randomization. Written voluntary informed consent in the presence of a witness will be taken

to ensure voluntary participation in the trial. After consent, LW will be randomized following the defined sampling strategy.

Related to notification of birth outcomes, VPT has a very robust surveillance system through which community health workers will notify the birth outcomes in the existing system through household PW follow-ups designed for this purpose. Moreover, for this trial to create liaison with the community, a very successful phone call system has been established through which the community is connected with a designated health worker 24/7. Therefore, any woman who delivers at any other facility or at home can also notify the study team through a phone call. An incentive has been established to encourage the family members to call within the time limit.

Once an LW with MUAC <23.0 cm and birth outcome captured within 0-6 days is identified, the LW will be counseled with regard to the trial procedure and will be given a time of 24-48 hours to discuss it with family members. Where required, randomization teams will visit the household to develop liaison with the family and explain the procedure. Once the woman and family demonstrate voluntary willingness, informed consent will be explained once again before the final signing of the consent in the presence of a witness. Following this, she will be randomized in one of the three arms according to the trial strategy.

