6.10. Assessment and Recording Data on Study Participants

The number of times each participant will be contacted for outcome assessment is summarized below (Table 4):

1. Maternal and infant anthropometry at birth (baseline, within 0-6 days of birth) and then on monthly basis until 6 months of age.
2. Every month, 24 hours food recall data will be collected from every enrolled LW

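### The SAP drops infant age at enrolment from the adjusted model without a reason, although baseline size is measured at any age from 0 to 6 days and birth weight has no stated source

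*SAP*

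**What the plan says.** **Adjusted model.** Protocol section 10 (Analysis approach) uses an ANOVA "with the model adjusted for the birth weight and age of the infants at enrollment". SAP section 12 runs one-way ANOVA with Tukey comparisons and then a general linear model in which "the analysis will be adjusted for the birth weight and length of infant, maternal MUAC at enrollment, maternal age, gravida", followed by "maternal body mass index and gender of child using general linear model (GLM"). Infant age at enrolment is not on the SAP list.

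**Baseline measurement.** Protocol 6.10 schedules "Maternal and infant anthropometry at birth (baseline, within 0-6 days of birth") and monthly measurements after that. The definitions in protocol section 10 also start both velocities from a measurement in the first 0-6 days, and protocol 7.3 places the first infant anthropometry at enrolment. SAP Table 2 has rows for infant weight and for infant age in hours, but none for birth weight.

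**Uses of birth weight.** It is an exclusion ("Newborns with a birth weight of less than 1500 grams" in SAP section 7; "VLBW i.e. < 1500 gram" in protocol 6.3), a covariate in both models, and the first subgroup in SAP section 13 ("Birth weight i.e. <2500 gm and => 2500 gm"). Neither document gives its source, and the covariate table in SAP 10.5 has no entry for it.

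**Consent pause.** Under protocol 6.5 a mother whose birth was captured on days 0-6 "will be given a time of 24-48 hours to discuss it with family members". Consent and randomisation follow.

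**The concern.** Two current documents specify different adjusted models for the primary outcome and for the main secondary growth outcomes. The covariate that differs is the one that records how old the infant was when first measured. Newborn weight is assumed here to change over the first days (the documents give no figure), so two infants of the same birth weight can enter with different baseline weights because of visit day alone. Baseline weight and length are the starting points of the velocities. If the baseline weight also serves as birth weight, it decides the side of the 2500 g cut.

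At stake are an unambiguous adjusted model, some precision (mainly for growth velocity) and the meaning of the label on the birth-weight subgroup.

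**Working it through.** **1. The plan's own figure.** Protocol section 11 assumes a difference of 0.12 cm/month, SD 0.5, one-sided alpha 0.025 and power about 0.80. Then n = 2 × (1.960 + 0.842)² × 0.5² / 0.12² ≈ 273 per arm. With the t distribution this becomes 274, and 274 / 0.86 = 319. The stated 274, 319 and 0.801 reproduce. Nothing in this point disputes them. The SD of 0.5 is used in step 2.

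**2. Length velocity.** Assumptions: early growth g of 2 to 5 cm/month, mean velocity 2.8 cm/month over 177 days, and age at baseline spread evenly. With baseline on day d,

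v = (2.8 × 177/30.4 − g × d/30.4) / (177 − d) × 30.4.

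- Day 6 instead of day 0: the shift runs from +0.03 (g = 2) to −0.08 cm/month (g = 5).
- Day 8: the shift runs from +0.04 to −0.10 cm/month.
- Largest day 0-6 case: SD = 0.077/√12 = 0.022, and 0.022²/0.5² ≈ 0.2% of the variance. If ages ran to day 8 it would be (0.104/√12)²/0.25 ≈ 0.4%.

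Even if age explained 1% of the variance, restoring it would raise power with 274 per arm only from 0.802 to 0.806.

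**3. Growth velocity.** In weight-ratio form over 175 days, a baseline that is a fraction L below birth weight shifts one infant's value by −1000 × ln(1 − L)/175.

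| Assumed loss L | Shift, g/kg/day |
|---|---|
| 3% | 0.17 |
| 5% | 0.29 |
| 7% | 0.41 |
| 10% | 0.60 |

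A shift common to all infants cancels between arms, so only its spread matters. With losses even over 0-7%, SD ≈ 0.41/√12 = 0.12. Variation in birth weight alone (assumed SD 400 g, mean 2757 g) contributes about 1000 × (400/2757)/175 = 0.83. The ratio of variances is 0.12²/0.83² ≈ 2%.

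**4. The 2500 g cut, if the enrolment weight is used.** Birth weight is assumed normal, with 26% below 2500 g (the national figure in protocol 1.1) and SD 400 g, which gives a mean of 2757 g. Added share = Φ((2500/(1 − L) − 2757)/400) − 0.26.

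| Assumed weight change at weighing | Net added share below 2500 g |
|---|---|
| Every infant has lost 3% | 6.6 points |
| Every infant has lost 5% | 11.7 points |
| Every infant has lost 7% | 17.1 points |
| Every infant has lost 10% | 26.0 points |
| Losses even over 0-5% | 5.6 points |
| Even from 5% loss to 5% gain | 0.5 points |

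The last row is a net figure. About 5.6/2 = 2.8 points move below the cut and about 2.3 move above it. With SD 500 g the uniform 5% case gives 9.2 points, so for 957 infants that case spans about 88 to 112.

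**5. The 1500 g exclusion.** A 5% loss moves the effective limit to 1500/0.95 = 1579 g. The share below it rises from 0.08% to 0.16% (SD 400 g) or from 0.41% to 0.65% (SD 500 g). That is about 0.1-0.2% of infants, or one or two in 957.

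**6. Entry window.** Capture on day 6 plus 48 hours puts enrolment at about day 8. The protocol still places the baseline measurement within days 0-6, and SAP 10.1 and 10.2 count elapsed time from the date of enrolment.

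**The case against.** The strongest reply is that little depends on this. Randomisation makes visit day non-differential, velocities are divided by elapsed days, z-scores are standardised for age, and the SAP model already contains baseline length. If birth weight is in fact the enrolment weight, that weight is itself a covariate. The subgroup analysis is only listed as potential. All of this stands and is why the severity is minor. It does not explain why the SAP leaves out a covariate that the protocol names and the trial collects.

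A reader might infer four stronger points that the documents do not support:

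- **That infants are weighed after day 6.** The pause makes later enrolment possible, but the documents place the measurement within 0-6 days. The gap is unreconciled; late weighing is not shown.
- **That no delivery weight exists.** None is scheduled, but SAP 10.5 collects delivery details at baseline, and the case report forms are not among the documents. What can be said is that the source is unstated.
- **That a 0.41 g/kg/day shift rivals the hypothesised 0.4 difference.** The first is a shift in one infant and cancels between arms. The second is a difference between arm means.
- **That a low-birth-weight effect cannot be read from the subgroup.** Even if every infant had lost 5%, 26/38, or about 69%, of the group below 2500 g would be truly low birth weight. That is dilution.

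**Conclusion.** The point holds as a minor one. The protocol and SAP disagree on the adjusted model, the omitted covariate is collected, and no reason is given. That rests on the text alone.

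The sizes rest on assumptions, because the documents give no early weight-change or early-growth data. There is no bias between arms. The effect on length velocity is about 0.2% of variance or less for baselines on days 0-6. The added spread in growth velocity is about 0.12 g/kg/day for losses over 0-7%. If enrolment weight is used as birth weight, the net shift at 2500 g is roughly 0.5 to 12 points for assumed changes within 5%. The upper end needs every infant to have lost 5%, and only larger uniform losses exceed it. The effect at 1500 g is negligible. The sample size is unaffected.

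**What to change.** **Main change.** In SAP section 12, add infant age at the baseline measurement to the adjusted model, as protocol section 10 has it, in hours or by day category. A day category avoids assuming that early weight change is linear in age. If the omission was deliberate, state the reason. The cost is one covariate already collected (a few degrees of freedom if by day). Make the change before the allocation code is revealed.

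**Secondary wording points.**

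- State the source of birth weight and the latest age at which it may be measured. If it is the enrolment weight, label the covariate and the 2500 g subgroup as weight at enrolment. The subgroup can then no longer be called low birth weight. Any change to the wording of the exclusion must be matched between SAP section 7 and protocol 6.3.
- Reconcile the 24-48 hour pause in protocol 6.5 with the 0-6 day baseline. Say whether elapsed time in SAP 10.1 and 10.2 runs from enrolment or from the measurement, should the two dates differ.

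None of this needs new data.

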¶ Wasting was defined as a weight-for-height z score lower than -2 SD.

[figure not shown]
|| Underweight was defined as a weight-for-age z score lower than -2 SD.

Table 3 | Outcomes at 6 months in the Intention-to-treat analysis*

[figure not shown]
Outcomes	Standard of care and only exclusive breastfeeding counselling	BEP with standard of care and exclusive breastfeeding counselling	BEP plus single dose of azithromycin to infant with standard of care and exclusive breastfeeding	Pairwise comparison $\Delta \pm SD$	p-value
	N=	N=	N=		
Primary outcomes - Mean					
Length velocity of infant (cm/mon)					
Secondary outcomes					
Infant related					
Growth – Mean					
Growth velocity (gm/kg/day)					
Mid-upper-arm-circumference (cm)					
Head circumference (cm)					
Length-for-age z-score					
Weight-for-age z-score					
Weight-for-length z-score					
Head circumference-for-age z-score					
Nutritional status - no./total no. (%)					
Wasting					
Stunting					
Underweight					
Adverse event - no./total no. (%)					
Infant deaths					
Hospitalization					
Injectable therapy					
Maternal related					
Nutritional status - Mean					
Maternal weight gain (kg)					
Mid-upper-arm-circumference (cm)					
Body mass index (kg/m ²)					
Adverse event - no./total no. (%)					
Infant deaths					
Hospitalization					
Injectable therapy					

* Plus–minus values are means \pm SD.

Figure 2 | Monthly trends for z-scores
2a | Monthly mean length-for-age z-scores

2b | Monthly mean weight-for-age z-scores

2c | Monthly mean weight-for-length z-scores

[figure not shown]

Table 4 | Subgroup analysis

Indicator	1	2	3	Δ	P-value	1	2	3	Δ	P-value	1	2	3	Δ	P-value	1	2	3	Δ	P-value	1	2	3	Δ	P-value					
Subgroups	Mean length velocity (cm/mon)					Weigh gain (gram/month)					Mean MUAC					Mean length-for-age z-score					Mean weight-for-length z-score					Mean weight-for-length z-score				
Maternal MUAC	< 21.0 cm																													
	=>21.0 cm																													
Maternal BMI	<18.5																													
	=>18.5																													
Birth weight	<2500 gm																													
	=> 2500 gm																													
Maternal age	<30 years																													
	=> 30 years																													
Gravidity	<3																													
	=>3																													
Gender	Male																													
	Female																													

References

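### The subgroup plan has no interaction test and Table 4 appears to give a P-value within each level, so a significant/non-significant contrast is likely to be read as effect modification

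*SAP*

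**What the plan says.** SAP section 13 opens with "The following variables will be considered for sub-group analysis for primary and secondary outcomes". It then gives two levels each for birth weight, maternal MUAC, maternal age, gravidity, maternal BMI and sex of the child. It names no test.

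The only other specification is the shell headed "Table 4 | Subgroup analysis" in SAP section 17. It has 12 level rows, and its header begins "Indicator 1 2 3 Δ P-value". The block of three arms, a difference and a P-value appears five times, under six outcome headings. One of those headings, weight-for-length z-score, appears twice.

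SAP section 12 uses one-way ANOVA for the arm comparison and adds that "Tukey's test will be used for multiple comparisons". All six subgroup variables also appear there as GLM adjustment covariates, and "For covariate adjustment, an unadjusted and stepwise adjusted model will be run". No product of arm and covariate is mentioned. The protocol contains no subgroup plan. Neither document calls the subgroup results exploratory or limits how they may be read.

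**The concern.** A subgroup analysis asks whether the arm effect differs between levels. A P-value inside each level answers another question: whether the arms differ in that level. With only within-level P-values, the natural step is to contrast a level below 0.05 with one above it. That contrast depends on the size of each level and on chance, and it arises often when the effect is the same in both.

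Two separate errors are possible:

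- **No effect anywhere:** a small P-value in a level is a false treatment effect.
- **The same effect in both levels:** the significant level is a true positive, and the error lies in concluding that the other level does not benefit.

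Adjusting for a variable as a main effect addresses neither error, because it does not test effect modification. Tukey's method covers pairs of arms and is not extended to subgroups or outcomes. The protocol's rationale says the trial is meant to inform public health policy, so a mistaken statement about which mothers or infants benefit would matter.

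**Working it through.** **Inputs.** The effect is 0.12 cm/month (SAP section 6: "effect size of difference of 0.12 cm per month between the arms"). The protocol section 11 table reads "Length Velocity 0.12 0.5 0.025 0.14 274 319 0.801", that is, SD 0.5, alpha 0.025 (one-sided), 14% dropout, 274 per arm, 319 after dropout and power 0.801. The documents give no subgroup prevalences, so the splits below are assumptions.

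**Plan's own figure.** SE = 0.5 × √(2/274) = 0.0427, and 0.12/0.0427 = 2.81. Power is Φ(2.81 − 1.96) = 0.802 by the normal approximation and 0.801 by noncentral t. 274/0.86 = 318.6, so 319. The design reproduces.

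**Number of P-values.** 12 rows × 5 column blocks = 60; 12 rows × 6 headings = 72. With no effect, the expected number below 0.05 is 60 × 0.05 = 3.0 to 72 × 0.05 = 3.6. This expectation does not require independence.

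**Length velocity alone, no effect.** There are 12 P-values. If they were independent, P(at least one < 0.05) = 1 − 0.95^12 = 0.46. But the six variables re-divide the same infants. A simulation used three arms of 274, six independently generated factors and a one-way ANOVA in each level. It gives about 33% (34% at 50/50 and 33% at 25/75 in 1,000 runs; 33% at both in 10,000 runs).

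**Same true effect of 0.12 in both levels.** For one active arm against control, with n completers per arm in a level, power = Φ(0.12/[0.5√(2/n)] − 1.96). P(exactly one level significant) = p1(1 − p2) + p2(1 − p1).

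| Assumed split | n per arm in each level | Power in each level | Exactly one significant |
|---|---|---|---|
| 50/50 | 137 / 137 | 0.511 / 0.511 | 0.50 |
| 25/75 | 68.5 / 205.5 | 0.289 / 0.682 | 0.58 |
| 10/90 | 27.4 / 246.6 | 0.142 / 0.760 | 0.69 |

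For example, at 25/75: 0.289 × 0.318 + 0.682 × 0.711 = 0.577.

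**Across all six variables.** The same simulation was run with both active arms 0.12 above control in every level. At least one variable has one level below 0.05 and the other not in 87% of trials at 50/50 and 93% at 25/75 (1,000 runs; 86% and 94% in 10,000). No effect modification exists in these simulated trials.

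**What an interaction test can do.** SE = 0.5 × √(2/n1 + 2/n2). At 50/50 this is 0.5 × √(4/137) = 0.0854. Two-sided 0.05 power for a 0.12 difference in effect is Φ(0.12/0.0854 − 1.96) = 0.29. It is 0.23 at 25/75 and 0.13 at 10/90. The difference detectable with 80% power is 2.80 × SE = 0.24, 0.28 and 0.40 cm/month respectively. Six interaction tests at 0.05 with no interaction give 1 − 0.95^6 = 0.26 if independent (24% to 28% simulated).

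**The case against.** **Table layout.** Table 4 is an empty shell read from a PDF, so a P-value cell merged across the two levels of a variable cannot be fully excluded. This stands as a limit on certainty about the layout, and it is why the count is a range. The per-row reading is still the more natural one, because the P-value follows three arm columns and a difference. Under either reading, no text defines an interaction test.

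**Choice of test.** The power figures use a two-arm one-sided test, whereas SAP section 12 names ANOVA and Tukey. At 137 per arm, with both active arms at 0.12, three-arm ANOVA has 52% power, and exactly one level is significant 2 × 0.52 × 0.48 = 50% of the time. A Tukey pairwise comparison has 36% power, giving 2 × 0.36 × 0.64 = 46%. The conclusion does not depend on the choice.

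**Importance.** The section is headed as potential analysis and its variables are only to be considered. That stands: the work is secondary and the primary analysis is untouched. But a full table shell is planned, and nothing restricts its interpretation.

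**Stronger readings the documents do not support.** A reader might infer that the table is bound to produce false claims even with no effect. For length velocity, the simulation leaves about a 67% chance of no within-level P-value below 0.05. A reader might also infer that subgroup results will decide who receives the supplement; no passage says so. That the contrast will be misread is a prediction about readers, so likely is the right word.

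**Conclusion.** The point holds as a gap in the analysis plan. Six two-level subgroup variables are listed without a test, the table shell appears to give within-level P-values, and no interaction test exists in either document. As planned, the output cannot answer the subgroup question.

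The size depends on the scenario. If the design effect is real and uniform, a contrast of one significant and one non-significant level is expected for any one variable in about half to two-thirds of trials, and for at least one of the six variables in most trials. If there is no effect, the chance of at least one small P-value for length velocity is about 33%; the 46% figure needs independence that the shared infants rule out.

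These figures rest on SD 0.5, 274 completers per arm, assumed splits and, in the simulation, factors independent of one another. The missing interaction test is certain; the exact number of P-values in Table 4 is not. It should be corrected before the subgroup results are produced.

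**What to change.** In SAP section 13, state that each of the six variables will be examined by adding an arm-by-subgroup interaction term, with the two-level main effect, to the adjusted GLM of section 12. In Table 4, replace the within-level P-values with one interaction P-value per variable and outcome. Give the pairwise arm differences with 95% CIs in each level. Label the whole analysis exploratory, and say that a difference in significance between levels will not be taken as evidence of a difference in effect.

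The cost is SAP and table-shell wording plus a few more model fits, with no new data and no change in sample size. The downside is that interaction power is low, so fewer subgroup statements will be possible and a non-significant interaction must not be read as proof of a uniform effect. Six interaction tests per outcome still carry about a 26% chance of one false positive, which is why the exploratory label is needed.

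Separately, the sponsor should check the repeated weight-for-length heading in Table 4. The documents do not settle whether it is a clerical slip or which outcome was intended.
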